#### • Iron Use

#### Dose of i.v. iron during the treatment period

Average quarterly i.v. iron dose (See Section 10.6.3) will be summarized using mean, standard deviation, minimum, P25, median, P75, and maximum. Quarter 1 (Day 1 to Week 12) and Quarter 2 (Week 12 to Week 24) will be used. This will be also summarized by baseline dialysis status.

#### Number (%) of subjects who use iron during the treatment period

The number and percentage of subjects who use iron (both i.v. and oral iron) during the treatment period will be summarized. This will be also summarized by baseline dialysis status.

#### • Iron Parameter (ferritin, TSAT, hepcidin, serum iron, and TIBC)

Based on literature review the distributions of TSAT and hepcidin are skewed and require a log-transformation (See Section 10.6.3).

#### Raw observed value at each assessment visit

Ferritin, serum iron, and TIBC values will be summarized using mean, standard deviation, 95%CI, minimum, P25, median, P75, and maximum at each assessment visit. TSAT and hepcidin values will be summarized using geometric mean, standard error, coefficient of

variation, and 95%CI based on log-transformed parameters, and median, minimum, and maximum based on original scale at each assessment visit. This will be also summarized by baseline dialysis status.

#### Change from baseline at each assessment visit

Change from baseline in Ferritin, serum iron, and TIBC values will be summarized using mean, standard deviation, 95%CI, minimum, P25, median, P75, and maximum at each assessment visit. Percent Change from baseline in TSAT and hepcidin values will be summarized using geometric mean and 95%CI based on log-transformed parameters, and median, minimum, and maximum based on original scale at each assessment visit. Graphical summarizes will be provided using mean and 95% CI over time. This will be also summarized by baseline dialysis status.

#### • Dose adjustment

The dose adjustment algorithm is described in Section 10.6.3, based on HemoCue Hgb values including those in both scheduled and unscheduled visits

## Dose level (mg) at each assessment visit

The values will be summarized using mean, standard deviation, minimum, P25, median, P75, mode, and maximum at each assessment visit. The mean dose during Week 12 to 24 will also be summarized. This will be also summarized by baseline dialysis status.

#### Duration (days) of treatment interruption due to Hgb >13.0 g/dL

The number and percentage of subjects who have a period of treatment interruption due to Hgb >13.0 g/dL will be summarized. On subjects who have a period of treatment interruption due to Hgb >13.0 g/dL, the duration (in days) of treatment interruption due to Hgb >13.0 g/dL per subject will be summarized using mean, standard deviation, minimum, P25, median, P75, and maximum. Hgb values observed in both scheduled and unscheduled visits will be counted in the summary. This will be also summarized by baseline dialysis status.

#### Dose adjustment

The number and percentage of subjects with dose adjustments will be provided. Number of dose adjustments will be summarized using mean, standard deviation, minimum, median, mode, and maximum. For dose adjustments frequency, the number and percentage of subjects will be provided by the number of dose adjustments (i.e. zero, one, two, three, four, and five or more). For timing of dose adjustments, the number and percentage of subjects with dose adjustments by each assessment visit will be provided. This will be also summarized by baseline dialysis status.

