4.3. Target Population and Sample Size

This study will enrol at least 22 Japanese HD patients with renal anemia not using ESAs. Assuming a 25% drop-out rate during the screening period, approximately 30 patients should be screened.

Assuming a 20% drop-out rate after the start of study treatment, the number of subjects who complete the 24-week study treatment is estimated to be 17.

Table 1 Target Sample Size

Screened	30
Enrolled	22
Completed fixed-dose period (Week 4)	20
Completed dose adjustment period (Week 24)	17

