6.3. Treatment Schedule

Starting dose (Day 1 to Week 4)

In the Japanese HD patients not using ESAs enrolled in the study, oral administration of GSK1278863 once daily at the starting dose of 4 mg will be started (Day 1), and continued until the day of Week 4.

Maintenance Dose (Week 4 to Week 24)

From Weeks 4 to 24, interruption of treatment or dose adjustments will be made within the maintenance dose range of 1-24 mg (Table 4) according to the dose adjustment algorithm (Table 5) to achieve and/or maintain Hgb within the target range (10.0-12.0 g/dL) based on the HemoCue Hgb value measured every 4 weeks. Dose changes will be made every 4 weeks. If any of the one-step dose reduction criteria is met during treatment at the minimum maintenance dose (1 mg), treatment should be interrupted; once the one-step dose increase criteria are met, treatment at 1 mg will be resumed. If the one-step dose increase criterion is met during treatment at the maximum maintenance dose (24 mg), treatment at 24 mg should be continued.

Table 4 Maintenance Dose of GSK1278863

Dose step	1	2	3	4	5	6	7	8
Dose level of GSK1278863 (once daily)	1 mg	2 mg	4 mg	6 mg	8 mg	12 mg	18 mg	24 mg
Number of GSK1278863 tablets taken	1 mg tablet ×1	2 mg tablet ×1	4 mg tablet ×1	6 mg tablet ×1	4 mg tablet ×2	6 mg tablet ×2	6 mg tablet ×3	6 mg tablet ×4

Table 5 Dose Adjustment Algorithm (GSK1278863)

Hgb (g/dL)	Hgb increase over 4 weeks (g/dL)	Treatment
>13.0	NA	Interrupt treatment until Hgb decreases to less than 12.0 g/dL Resume treatment at the one lower dose level (resume treatment at 1 mg once the one-step dose increase criteria are met, if interrupted at 1 mg)
12.0-13.0	NA	One-step dose reduction
10.0-<12.0	>2.0	One-step dose reduction
	≤2.0	Continue treatment at the current dose level
7.5-<10.0	>2.0	One-step dose reduction
	0.5-2.0	Continue treatment at the current dose level
	<0.5	One-step dose increase
<7.5	NA	Discontinue treatment permanently * and initiate another appropriate treatment

*: If an initial Hgb value is less than 7.5 g/dL, measurement will be repeated at the same study visit (using the same sample) to calculate the average. If the average meets the Hgb stopping criteria, study treatment will be discontinued.

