## 8. SECONDARY STATISTICAL ANALYSES

## 8.1. Secondary Efficacy Analyses

## 8.1.1. Overview of Planned Secondary Efficacy Analyses

The secondary efficacy analyses will be based on the All Treated Subjects population, unless otherwise specified.

Table 4 provides an overview of the planned secondary efficacy analyses, with further details of data displays being presented in Appendix 14: List of Data Displays.

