#### Dose Adjustment

#### Dose adjustment algorithm

- Dose Adjustment algorithm will be based on HemoCue Hgb values at scheduled visits. No Hgb values measured at unscheduled visits will be included.
- Dose will be derived from prescribed dose recorded in eCRF, not actual dose associated with container numbers.
- The following table illustrates the algorithm using analysis flags as below:
  - (FL\_A): Adjustment flags will be counted if prescribed dose recorded in eCRF is changed from that of the previous visit.
  - (FL\_B): Over 13 g/dL flags will be counted if HemoCue Hgb >13 g/dL is observed.
  - (FL\_C): Interruption flags will be counted if prescribed dose recorded in eCRF is zero. Treatment durations will be calculated based on the following formula:
    - Duration (days) = Treatment Stop Date Treatment Start Date + 1

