#### 204716

#### CONFIDENTIAL

Dose A	djustment								
		15MAR2017							
	Week 8	02APR2017/	30	11.8	2	Y	N	N	
		01MAY2017							
	Week 12	02MAY2017/	31	13.4	0	Y	Y	Y	
		01JUN2017		44.0		N (			
	Week 16	02JUN2017/ 01JUL2017	30	11.6	1	Y	N	N	
	Week 20	02JUL2017/	31	12.7	0	Y	Ν	Y	
		01AUG2017							
	Week 24	-	-	12.3	-	-	Ν	-	

 
'Dose adjustment'
 
Duration (days) of treatment interruption due to Hgb >13 g/dL
 
									
Calculation of duration of treatment interruption due to Hgb >13 g/dL will be based on the above									
algorithm and the below formula.									

 
Duration (days) = Sum of [Duration]n
 
									
	where								
	[Duration]₀ represents exposure duration at visit n.								
If over 13 g/dL flag (FL_B) = 'Y' and interruption flag (FL_C) = 'Y':									

 
Duration (days) = Treatment Stop Date - Treatment Start Date + 1
 
									
If else:									

 
Duration (days) = 0
 
									
Frequency of dose adjustment									
Calculation of frequency of dose adjustment will be based on the above algorithm.									

 
Number of dose adjustment will be counted for each subject as follows:
 
									

 
Counts of adjustment flag = 'Y'
 
									
Number of dose adjustment to reach the lower Hgb target (10.0 g/dL)									
Number of dose adjustment to reach the lower Hgb target will be counted for each subject as follows									
• Counts of adjustment flag ='Y' at visits before Date to reach the lower Hgb target, including a record which firstly achieved the lower Hgb target.									

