8.1 Secondary Efficacy Analyses	
 
Added summaries of number of dose adjustment to reach the lower Hgb target Hgb level (10.0 g/dL)
 
For the summary of time to reach the lower target Hgb level, modification was made to include all subjects in the analysis.
 
	
 
This will facilitate review of the study results
 
Correction according to team discussion
 

8.1.2 Planned Efficacy Table Displays	
 
Text added to clarify that the analysis of scatter plot includes Pearson's correlation coefficient.
 
Updates were made to the summaries of dose level (mg) for adding P25 and P75.
 
In dose adjustment summary, it has been re-corrected that all subjects including those with no dose adjustment will include a summary.
 
	
 
Clarification
 
These will facilitate review of the study results.
 
Reconsideration clinically for the dose adjustment summary.
 

8.2 Safety Analyses 10.14 Appendix 14: List of Data Displays	Added additional tables: • On-therapy Serious Drug-Related AEs • On-therapy Non-Serious Drug-Related AEs	Required for a Plain Language Summary (PLS) for GSK
10.4.1 Treatment States	Clarification has been made for treatment states of follow-up visit assessments.	Clarification
10.6.1 General	
 
Updates were made for definitions of treatment states; use study treatment stop date instead of end of treatment date (EoT). In addition to general changes of the treatment states due to this, note that this change has impact on the following endpoints for specific derivations:
 
Time (in days) to reach the lower target Hgb level (10.0 g/dL)
 
Dose of i.v. iron during the treatment period
 
	For daprodustat, the treatment states will be more explainable on the basis of study treatment stop date derived from the exposure record rather on the basis of EoT derived from the assessment visit.
10.6.2 Study Population	Text added for treatment compliance up to Week 4.	Compliance up to Week 4 will facilitate review of the study results.
10.6.3 Efficacy	Deleted text that mentioned the baseline Hgb value might include that at unscheduled visits.	Missing the Hgb value at Day 1 will never happen so that no need to mention the unscheduled visits for the baseline Hgb derivation.
10.6.3 Efficacy	Added the candidate covariates (body weight at screening and baseline Hgb) to provide the	This will facilitate review of

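### The frequency of dose adjustments is a raw count in all treated subjects, so its zero row mixes subjects with no dose record after Day 1 and subjects who stayed on 4 mg through all five decisions

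*SAP*

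**What the plan says.** - **Endpoint.** Protocol Section 3 lists the frequency of dose adjustments among three endpoints under a secondary objective about dose adjustment.
- **Schedule.** Protocol 6.3 holds the dose at 4 mg until Week 4; after that, "Dose changes will be made every 4 weeks". Table 6 shows dispensing at Day 1 and at Weeks 4, 8, 12, 16 and 20, so a completer passes five scheduled dosing decisions.
- **Population.** SAP 8.1.1: "The secondary efficacy analyses will be based on the All Treated Subjects population, unless otherwise specified". The display list gives the same population for Tables 2.45 and 2.46.
- **Display.** SAP 8.1.2 (Dose adjustment) asks for the share of subjects with any adjustment, summary statistics of the number, a distribution in which the number and percentage of "subjects will be provided by the number of dose adjustments (i.e. zero, one, two, three, four, and five or more", and adjustments by visit.
- **Derivation.** SAP 10.6.3: "Calculation of frequency of dose adjustment will be based on the above algorithm". The flag rule there is "Adjustment flags will be counted if prescribed dose recorded in eCRF is changed from that of the previous visit", and a subject's number is "Counts of adjustment flag = 'Y". In the SAP's worked illustration, the Day 1 row is flagged N, and the Week 24 row, which has no dose, carries no flag.
- **Who is included.** The V1.2 entry in Appendix 16 agrees with the current text: "all subjects including those with no dose adjustment will include a summary".
- **Planned attrition.** Protocol 4.3, Table 1: 22 enrolled, 20 in the row "Completed fixed-dose period (Week 4", and 17 completing Week 24.

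**The concern.** A count of events means little without the number of occasions on which the event could occur. Here that number runs from none (a subject with only a Day 1 dose record) to five (a completer), and the derivation ignores it.

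The zero row therefore holds two kinds of subject. Some passed five decisions and stayed on 4 mg. Others have no dose record after Day 1, because they left before Week 4 or because treatment was permanently stopped at the Week 4 visit and no new dose was prescribed. A reader cannot tell them apart in that row. Subjects who leave later can still score changes, but have fewer chances to do so.

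The distortion runs one way: incomplete follow-up can only lower a subject's count. At stake is an accurate description of how often the dose had to be changed, which is a stated secondary endpoint.

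**Working it through.** **1. The planning figures hold together.** The documents give no expected number of adjustments, so there is no figure to reproduce for this endpoint. The attrition figures can be checked: 30 × 0.75 = 22.5 (22 stated) and 22 × 0.80 = 17.6 (17 stated). Protocol 9.2.1 uses the same 20 subjects at Week 4, and its half-width reproduces: 2.093 × 1.5 / √20 = 0.702 g/dL.

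**2. Subjects in the zero row by construction.** 22 − 20 = 2 are planned to leave before Week 4. With only a Day 1 record, neither can be flagged: 2/22 = 9.1%.

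**3. Effect on the zero share.** Let k be the number of the 20 subjects reaching Week 4 who have no adjustment. The comparison is k/20 among those 20 against (k + 2)/22 as planned:

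(k + 2)/22 − k/20 = (40 − 2k)/440 = (1/11)(1 − k/20), that is, 9.1 × (1 − k/20) percentage points.

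The documents do not give k, so the range is shown:

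| k | Among the 20 | As planned (of 22) | Difference (points) |
|---|---|---|---|
| 0 | 0% | 9.1% | 9.1 |
| 4 | 20% | 27.3% | 7.3 |
| 8 | 40% | 45.5% | 5.5 |
| 12 | 60% | 63.6% | 3.6 |
| 16 | 80% | 81.8% | 1.8 |
| 20 | 100% | 100% | 0 |

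With one or three early leavers instead of two, the maximum is 1/22 = 4.5 or 3/22 = 13.6 points.

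**4. Effect on the mean.** If the 20 subjects have S adjustments in total, their mean is S/20 and the planned table shows S/22. The ratio is 20/22 = 0.909, a fall of 9.1% whatever S is.

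**5. Later leavers.** The 20 − 17 = 3 further losses also have incomplete follow-up. If each passed one to four decisions, the total is 17 × 5 + 3 × 1 = 88 to 17 × 5 + 3 × 4 = 97, out of 22 × 5 = 110 (80.0% to 88.2%). The extremes are 85 (all three stop at the Week 4 visit with no new dose) and 100 (all three leave after Week 20). How many adjustments this removes cannot be computed without an adjustment rate.

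**6. Treatment of early leaving in neighbouring displays.** The dose-level-by-visit table has an early-withdrawal category. The mean-dose figures drop subjects with fewer than three dosing records. Time to the lower target is censored at treatment stop. The number of adjustments needed to reach that target excludes subjects who never reach it. The overall adjustment count has no such rule.

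**The case against.** **The leavers are visible elsewhere.** By-visit timing is part of this same summary. The dose-level table has its withdrawal category, days on drug are banded from 1–28 days, discontinuations are tabulated with reasons, and Figure 2.11 plots each subject's Hgb and dose. With about 22 subjects, a reader could trace every zero. This stands, and it lowers the priority of the point. It does not correct the printed mean or zero row.

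**Including everyone was deliberate.** The V1.2 log records a clinical reconsideration, and the study is descriptive with no hypothesis tests. A count in all treated subjects is a fair record of what happened. This also stands, and is why the All Treated count should be kept and not replaced.

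**The denominator is not printed.** The mock shells are in separate documents. All Treated Subjects is the natural reading of the text, not an explicit statement for this row.

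**Three stronger readings go beyond the documents.**

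- *That the zero row makes the 4 mg start look adequate.* The starting dose is assessed on Week 4 Hgb change and its categories (SAP 7.1.2). The adjustment count serves another objective, and nowhere is zero adjustments over 24 weeks treated as evidence about the start.
- *That the two planned early leavers are treatment failures.* Entry requires Day 1 Hgb of at least 8.0 g/dL, and no HemoCue test is scheduled between Day 1 and Week 4. At scheduled visits, a confirmed value below 7.5 g/dL can first appear at Week 4, after those two have left. A subject stopped at that visit would also score zero, but Hgb below 7.5 g/dL has its own table and listing.
- *That the zero row is inflated two- to threefold.* This needs an assumed chance of change per decision and a comparator in which all 22 subjects make five decisions, which the plan never sets. With an independent 40% chance, five decisions give 0.6⁵ = 7.8%. The planned table gives (2 + 3 × 0.6⁴ + 17 × 0.6⁵)/22 = 16.9% if the three later leavers had four decisions each, or 23.3% if one each. Protocol 4.5 says response varies greatly between subjects. Let the chance vary around the same 40% average, for illustration as Beta(0.8, 1.2). Five decisions then give 0.6 × (2.2/3) × (3.2/4) × (4.2/5) × (5.2/6) = 25.6%, and the planned table gives 32.9% to 37.1%, a ratio of only 1.3 to 1.4. The documents fix neither figure.

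**Conclusion.** The point holds as a limited defect in how one secondary endpoint is described. Subjects with no dose record after Day 1 are scored as zero adjustments by rule, and later leavers have fewer chances to score.

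Under the planned attrition, relative to subjects who reach Week 4, this adds between 0 and 9.1 points to the zero share, depending on k, and lowers the mean by 9.1%. In the dialysis-status split (Table 2.46) one early leaver weighs more, because the groups are smaller.

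The size rests on three things: two of 22 leaving before Week 4 as planned, All Treated Subjects as denominator, and no new dose being recorded for a subject stopped at Week 4. The primary assessment of the starting dose is not directly affected. This is a cheap improvement to the table.

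**What to change.** In SAP 8.1.2 and 10.6.3 (Tables 2.45 and 2.46), keep the All Treated count and make two additions.

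1. Split the zero row into three:
   - zero, all five scheduled dosing decisions reached;
   - zero, stopped earlier after at least one further dose record;
   - no dose record after Day 1.
2. Report adjustments per scheduled dosing decision reached, with the total number of decisions as denominator and the numerator counted at the same scheduled visits.

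Define a decision as reached when a prescribed dose, including 0 mg, is recorded at Week 4, 8, 12, 16 or 20. State how a subject with a missed intermediate visit is classified, and print the denominator in the shell.

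Do not replace the All Treated distribution with one limited to subjects reaching Week 20: that conditions on staying on treatment and brings its own selection.

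The cost is a few sentences of SAP text and a few table rows from exposure records already collected. No data collection or clinical rule changes.

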#### Number (%) of subjects with each dose level at each assessment visit

The number and percentage of subjects with each dose level adjustments will be provided. Graphical summaries will be provided with the number of subjects in each dose level. Dose level categories will be classified into 10; W/d (early withdrawal), 0 mg (treatment interruption), 1 mg, 2 mg, 4 mg, 6 mg, 8 mg, 12 mg, 18 mg, and 24 mg). This will be also summarized by baseline dialysis status.

### Number of dose adjustment to reach the lower Hgb target (10.0 g/dL)

The number and percentage of subjects with dose adjustments to reach the lower Hgb target will be provided on the basis of on-therapy Hgb. Number of dose adjustment to reach the lower Hgb target will be summarized using mean, standard deviation, minimum, median, mode, and maximum. For dose adjustments frequency, the number and percentage of subjects will be provided by the number of dose adjustments (i.e., zero, one, two, three, four, five or more). Subjects who does not reach the lower Hgb target during treatment period will be excluded from the summary. This will be also summarized by baseline dialysis status.

#### • Other

The following two sorts of scatter plots of interest will be produced for overall and dialysis status groups:

Change from baseline in Hgb at Week 4 versus the candidate covariates

Mean dose during Week 12 to 24 versus the candidate covariates

See Appendix 10 for the candidate covariates and Section 10.6.3 for the detailed derivations.

## 8.1.3. Planned Hgb Efficacy Statistical Analyses

Ş	Secondary Hgb Analyses
E	Endpoint(s)
	
 
Hgb and changes from baseline
 

	
 
Number (%) of subjects who have a Hgb level within the target range (10.0–12.0 g/dL)
 

	
 
Time (in days) to reach the lower target Hgb level (10.0 g/dL)
 

	
 
Number (%) of subjects who have a Hgb level of less than 7.5 g/dL
 

	
 
Number (%) of subjects who have a Hgb increase of more than 2.0 g/dL over any 4 weeks
 

	• Number (%) of subjects who have a Hgb level of more than 13.0 g/dL and number of episodes
I	Model Specification
	
 
Hgb values from central laboratory will be used, unless otherwise specified. However, if a central laboratory Hgb value is missing, a corresponding non-missing HemoCue Hgb value will be used (See Section 10.6.3).
 

•	• The secondary analysis is to assess appropriate control of Hgb within the target range, on the basis of the Hgb mean at Week 24 and the number (%) of subjects with Hgb within the target

#### Secondary Hgb Analyses

range as secondary endpoints.

- For the Hgb, the summary statistics will be calculated, along with the two-sided 95% confidence interval based on t-distribution.
- The percentage of subjects with Hgb within the target range will be calculated at Week 24, with calculation of exact two-sided 95% confidence interval based on binomial distribution.
- The time (in days) to reach first the lower target Hgb level (10.0 g/dL) will be calculated in each subject, and summarized descriptively by Kaplan-Meier method using P25, median, and P75. Subjects who could not reach lower target will be regarded as censored at Study Treatment Stop Date (See Section 10.6.1).

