5.1. Inclusion Criteria

A subject will be eligible for inclusion in this study only if all of the following criteria apply at provisional enrollment (Screening) and formal enrollment (Day 1) unless otherwise specified.

1. Age (at the time of informed consent): ≥ 20 years
2. Dialysis: Patients on HD or hemodiafiltration (HDF)
3. Use of any ESA:
 - Newly started dialysis (Dialysis newly started < 12 weeks before screening): Patients not using ESAs after the start of dialysis
 - Maintenance dialysis (Dialysis started ≥ 12 weeks before screening): Patients not using ESAs within 8 weeks before screening [including patients who are on treatment/interruption of ESA therapy and planned to interrupt ESA therapy for at least 8 weeks prior to Screening exam (at the time of informed consent)]
4. Hemoglobin (Hgb): ≥ 8.0 to < 10.0 g/dL [measured using a point-of-care Hgb measurement device (HemoCue) at the study site on Day 1]
5. Iron parameter: Ferritin > 100 ng/mL or TSAT $> 20\%$ (at screening only)
6. Gender (at screening only): Female or male
A female subject is eligible to participate if she is not pregnant (as confirmed by a negative serum human chorionic gonadotropin [hCG] test for females of reproductive potential [FRP] only), not breastfeeding, and at least one of the following conditions applies:
 - 1) Females of non-reproductive potential defined as:
 - Pre-menopausal with one of the following and no plans to utilise assisted reproductive techniques (e.g., in vitro fertilisation or donor embryo transfer):
 - documented bilateral tubal ligation or salpingectomy
 - documented hysteroscopic tube occlusion procedure with follow-up confirmation of bilateral tubal occlusion
 - documented hysterectomy
 - documented bilateral oophorectomy
 - Post-menopausal defined as 1) females 60 years of age or older or 2) In females < 60 years of age, 12 months of spontaneous amenorrhea [In questionable cases, a blood sample with simultaneous follicle stimulating hormone (FSH) and estradiol levels consistent with menopause is confirmatory (the reference values are provided separately)]. Females on hormone replacement therapy (HRT) and whose menopausal status is in doubt will be required to use one of the highly effective contraception methods if they wish to continue

their HRT during the study. Otherwise, they must discontinue HRT to allow confirmation of post-menopausal status prior to study enrollment.

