#### *Time (in days) to reach the lower target Hgb level (10.0 g/dL)*

The time (in days) will be summarized using P25, median, and P75 by Kaplan-Meier method. Kaplan-Meier plot of time to event will be provided using on-therapy Hgb values. Subjects who could not reach lower target will be regarded as censored. This will be also summarized by baseline dialysis status.

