#### 10.4.1.1. Treatment States for Hgb Data

Treatment State	Definition
Pre-therapy	Date ≤ Randomization Date
On-therapy	Randomization Date < Date ≤ Study Treatment Stop Date + 1 day
Post-therapy	Date > Study Treatment Stop Date + 1 day

NOTES:

• If Randomization date is missing then the assessment will be consider to be Pre-therapy

• If study treatment stop date is missing then the assessment will be considered to be On-therapy

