# **10.6.** Appendix 6: Derived and Transformed Data

### 10.6.1. General

Multiple Measurements at One Time Point			
• Mean of the measurements will be calculated and used in any derivation of summary statistics but if listed, all data will be presented.			
• Subjects having both High and Low values for Normal Ranges at any post-baseline visits for safety parameters will be counted in both the High and Low categories of "Any visit post-baseline" row of related summary tables. This will also be applicable to relevant Potential Clinical Importance summary tables.			
• For multiple measurements at Screening and Day 1 visit, the screening-pass visit record will be used for analysis (See Appendix 3).			
Study Day			

 
Calculated as the number of days from randomization date:
 
Ref Date = Missing → Study Day = Missing
 
Ref Date < Randomization Date → Study Day = Ref Date - Randomization Date → Study Day = Ref Date - (Randomization Date) +1
 
			
Unique Subject ID			

 
All subjects have unique subject ID for analyses even if a subject was enrolled after rescreened. Tables/figures/listings will be produced based on unique subject ID.
 
For a rescreened subject, the unique subject ID will be derived from the first-assigned subject number though he or she seems to have multiple subject numbers in eCRF records by screening assessment. The other subject numbers, which are to be recorded within a supplemental domain, will be associated with the unique subject ID.
 
			
Rescreening Subjects			

 
For rescreened subjects, data collected in screening-pass visit will be used for analysis. They may have multiple records at Screening and/or Day 1 visit, which associates with a screening-pass visit and screening failure visit(s)
 
Regarding a listing of SAEs in screening period, all pre-therapy SAEs captured in eCRF will be provided including screen failure records of rescreened subjects.
 
			
Study Treatment Start Date			
First randomized treatment start date			
Study Treatment Stop Date			
Latest end date of treatment			
• Note that the end date of treatment will be captured as the end date when subjects were intended to end the treatment, rather than when subjects have actually ended the treatment.			
Time Definitions (per GSK standard principles)			

 
1 week = 7 days
 
1 month = 30.4375 days
 
1 year = 365.25 days
 
			

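### Time to Hgb 10.0 g/dL: censoring subjects who stop treatment before target, including those stopped for low Hgb, raises the Kaplan-Meier curve and can bring its quartiles forward

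*SAP*

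**What the plan says.** SAP section 8.1.2 summarises time to the lower target by Kaplan-Meier P25, median and P75, and adds: "Kaplan-Meier plot of time to event will be provided using on-therapy Hgb values". Non-reachers are censored, and section 8.1.3 fixes the date: "Subjects who could not reach lower target will be regarded as censored at Study Treatment Stop Date". Section 10.6.1 defines that date as "Latest end date of treatment". For Hgb data, section 10.4.1.1 counts a value as on-therapy when "Randomization Date < Date ≤ Study Treatment Stop Date + 1 day".

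Protocol Table 5 (section 6.3) gives this action for Hgb below 7.5 g/dL: "Discontinue treatment permanently". Section 5.4 lists the same criterion, based on the average of repeated HemoCue readings at the visit. Section 4.3 plans 22 enrolled, 20 completing Week 4 and 17 completing Week 24: "Assuming a 20% drop-out rate after the start of study treatment".

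The SAP has no competing-event rule or sensitivity analysis for this endpoint. Section 10.7.2.2 covers only the use of a HemoCue value where the central-laboratory value is missing.

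**The concern.** Kaplan-Meier is unbiased for time to target only if a censored subject has the same future chance of reaching 10.0 g/dL as those still at risk. Here Hgb drives both the endpoint and one of the reasons for leaving the risk set. A subject withdrawn for Hgb below 7.5 g/dL is the furthest from target and is removed for that reason. Because values later than one day after the stop date are not on-therapy, that subject cannot have an event afterwards. Permanent discontinuation before target therefore acts as a competing event, not as loss of information.

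Each such removal spreads the subject's weight over those who remain, so the curve can only rise and the quartiles can only move earlier. The endpoint supports the objective of overall Hgb control. The study is single-arm, is described as one of the pivotal studies, and has about 22 subjects, so a few removals can shift a reported quartile by a whole 4-week visit.

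**Working it through.** **Inputs from the documents.** N = 22; Hgb visits at Weeks 4, 8, 12, 16, 20 and 24; 20% drop-out after the start of treatment; censoring at Study Treatment Stop Date.

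**Plan's own figure.** 22 × (1 − 0.20) = 17.6, against 17 stated. Table 1 implies 22 − 20 = 2 losses by Week 4 and 20 − 17 = 3 later, so five in all. The documents give no planned figure for time to target.

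**Does the stop date fall early for early stoppers?** A note in SAP 10.6.1 says the date captured is the intended rather than the actual end of treatment. I read this as the date set for that subject, not planned Week 24. SAP 10.6.3 supports this: for withdrawal before Week 12, it closes the first iron quarter at Study Treatment Stop Date.

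**Assumed.** The numbers reaching target at each visit and the times of the stops.

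**Formula.** Kaplan-Meier: F(t) = 1 − ∏(1 − d/n), with d subjects reaching target at a visit and n still at risk. If early stoppers stay in the denominator as not reached, F(t) is the cumulative number reaching target divided by 22. That equals the cumulative incidence with discontinuation competing, provided discontinuation is the only exit before Week 24.

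**Main pattern: 4, 3, 3, 2, 2, 1 reach target at the six visits (15 of 22).**

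- Stoppers kept as not reached: 4/22, 7/22, 10/22, 12/22, 14/22, 15/22 = 18.2%, 31.8%, 45.5%, 54.5%, 63.6%, 68.2%.
- One stop after Week 4: n = 22, 17, 14, 11, 9, 7. S = 18/22 × 14/17 × 11/14 × 9/11 × 7/9 × 6/7 = 0.289, so F = 71.1%.
- Three stops (one before Week 4, one after Week 4, one after Week 8): n = 21, 16, 12, 9, 7, 5. S = 17/21 × 13/16 × 9/12 × 7/9 × 5/7 × 4/5 = 0.219, so F = 78.1%.
- Five stops (two before Week 4, one each after Weeks 4, 8 and 12): n = 20, 15, 11, 7, 5, 3. S = 16/20 × 12/15 × 8/11 × 5/7 × 3/5 × 2/3 = 0.133, so F = 86.7%.

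| Stops before target | Week 24 curve | Rise over 68.2% | Median | P75 |
|---|---|---|---|---|
| Kept as not reached | 68.2% | – | Week 16 | not reached |
| 1 censored | 71.1% | 2.9 | Week 16 | not reached |
| 3 censored | 78.1% | 9.9 | Week 12 | Week 24 |
| 5 censored | 86.7% | 18.5 | Week 12 | Week 20 |

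Over three event patterns the rise was about 2 to 3 points with one stop, 7 to 11 with three and 13 to 23 with five.

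**Sensitivity to the pattern.**

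- With 5, 4, 3, 2, 1, 1 (16/22 = 72.7%) and the same five stops, S = 15/20 × 10/14 × 6/9 × 3/5 × 2/3 × 1/2 = 0.071, so F = 92.9%. P75 is Week 16 instead of not reached.
- Other spreads of 16 events (4, 3, 3, 2, 2, 2 or 4, 4, 3, 2, 2, 1) give P75 at Week 20 with those stops.
- With 5, 4, 3, 2, 1, 1 and one stop after Week 4, S = 17/22 × 12/16 × 9/12 × 7/9 × 6/7 × 5/6 = 0.241, so F = 75.9% against 72.7%. The median stays at Week 12, but P75 changes from not reached to Week 24.
- With 4, 3, 3, 1, 1, 1 (13 of 22) and five stops, the median is Week 12 against Week 16.

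**Completers who never reach target** are censored at about Day 168, after the last visit at which an event can occur. They stay in every denominator and add no bias.

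**The case against.** The strongest reply concerns size and stakes. The planned 20% drop-out covers all causes. Protocol 5.4 also lists transplant, pregnancy, cancer, liver chemistry and the subject's own request. Such stops need not depend on Hgb, and some would occur after target. One informative stop moves the curve by 2 to 3 points and left the median unchanged in the patterns tried. Protocol 9.4.1.2 bases the secondary analysis on Week 24 mean Hgb and the percentage in range; time to target is an added descriptive summary, with no test or comparator. Failures also appear elsewhere: the SAP tabulates and lists Hgb below 7.5 g/dL, reports discontinuation reasons, carries an early-withdrawal category in the dose tables and plots individual profiles. All this stands and limits the weight of the point. It does not correct the quartiles or the plot.

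A reader might go further in two ways that the documents do not support.

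- **An overstated success rate.** The SAP tabulates quartiles and a plot, not a Kaplan-Meier proportion at Week 24. A gap such as 92.9% against 72.7% needs all five drop-outs to stop before target, and it concerns a reading of the curve.
- **A favourable bias from subjects already at 10.0 g/dL at baseline.** Entry Hgb is "measured using a point-of-care Hgb measurement device (HemoCue) at the study site on Day 1", while efficacy uses the central laboratory, so a central baseline of 10.0 or more is possible. But no visible text assigns these subjects a Week 4 event, and SAP 10.6.3 is broken in the copy reviewed, so a rule may be lost. They would also have to be at 10.0 or more at Week 4: about 68 to 81% would be, assuming a mean change of 0.5 and SD of 1.0 to 1.5 g/dL and ignoring regression to the mean. The direction depends on the comparison. Against excluding them, time to target looks shorter; against an event on Day 1, it looks longer, and the quartiles were unchanged in the scenarios run.

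**Conclusion.** The point holds for subjects who stop treatment before target because of low Hgb. Censoring them at the stop date is informative, raises the Kaplan-Meier curve and can bring the quartiles forward, and no other part of the plan corrects it. In assumed patterns the Week 24 rise runs from about 2 to 3 points with one stop to 13 to 23 points with five, the last being an upper bound. Quartiles move by anything from nothing to a few 4-week visits, or change from not reached to reached. These sizes rest on assumed event and stop times and on reading Study Treatment Stop Date as early for early stoppers. Stops unrelated to Hgb may add no bias to the on-treatment rate. The endpoint is descriptive, so no error rate or sample size is affected. A favourable bias from baseline values at or above 10.0 g/dL is not established.

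**What to change.** In SAP 8.1.2 and 8.1.3, take P25, median, P75 and the plot from the cumulative incidence of first on-therapy Hgb of 10.0 g/dL or more, with permanent discontinuation before target as a competing event. Equivalently, keep early stoppers in the denominator as not reached to Week 24. State that a quartile is reported as not reached when the curve does not get there. Keep the current Kaplan-Meier curve as a sensitivity display, labelled as assuming that stoppers would have continued like those still treated. At most, add the same summary restricted to subjects with a central-laboratory baseline below 10.0 g/dL beside the all-subject one.

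The cost is a few lines of SAP text and a small programming change on data already collected. Time to target will look somewhat less favourable. Stops unrelated to Hgb will also count as not reached, which is why the Kaplan-Meier display is worth keeping.
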